Indolent non-Hodgkin lymphoma (iNHL)
o FL

 
Waldenström macroglobulinemia (WM)
 

o CLL/SLL
Multiple myeloma (MM)

 
Other B-cell malignancy (including but not limited to: Hodgkin's lymphoma, Burkitt lymphoma, marginal zone lymphomas, mediastinal large B-cell lymphoma, and hairy cell leukemia)
 

Under Amendment 3 of this protocol, subjects with MCL or iNHL (including FL, WM, and CLL/SLL) are no longer enrolled.
Under Amendment 4 of this protocol, subjects with RS are no longer enrolled.
Part 3
Part 3 includes up to 30 subjects with primary MF, post-polycythemia vera MF, or post-essential thrombocythemia MF with thrombocytopenia or anemia. Part 3 will run in parallel with Part 2. Subjects with MF will receive a run-in of 6 weeks of acalabrutinib alone. Subjects who are demonstrating a clinically meaningful response, in the opinion of the investigator, may continue on acalabrutinib monotherapy; those who are not will receive combination therapy with acalabrutinib and pembrolizumab.
In Part 3, safety and response data will be reviewed after the initial 12 subjects have completed 24 weeks of treatment (i.e., the Week 25 visit) or have discontinued treatment before Week 25. The first 12 subjects will be evaluated regardless of the length of treatment with acalabrutinib alone or in combination with pembrolizumab. If <2 subjects who received acalabrutinib monotherapy or the combination with pembrolizumab have achieved a response of "clinical improvement" or better (see Table 9), the MF group will not be expanded. The decision to expand the study is multifactorial and will take into consideration the nature and quality of response, safety, and evolving competitive landscape. If the safety and response data indicate that further evaluation is warranted, up to 18 additional

subjects with MF (for a total of up to 30 subjects) will be treated on the same adaptive regimen as was given to the first 12 subjects.
Under Amendment 3 of this protocol, Part 3 is closed to enrollment.

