determination of maximum tolerated dose (MTD). The trial employs the standard National Cancer Institute definition of MTD (dose associated with DLT in <33.3% of subjects). Provided ≤1 DLT occurs during the DLT review, then expansion will occur in Part 1 to include up to 24 subjects in a select group of histologies (as described in Section 3.0). The safety and preliminary efficacy results from Part 1 will be used to determine opening Part 2 and Part 3 of the protocol.
In Part 2, expansion groups of up to 30 subjects per disease type will be enrolled. In Part 3, safety and response data will be reviewed after the initial 12 subjects have completed 24 weeks of treatment (i.e., the Week 25 visit) or have discontinued treatment before Week 25. The first 12 subjects will be evaluated regardless of the length of treatment with acalabrutinib alone or in combination with pembrolizumab. If <2 subjects who received acalabrutinib monotherapy or the combination with pembrolizumab have achieved a response of "clinical improvement" or better, the MF group will not be expanded. The decision to expand the study is multifactorial and needs to take into consideration the nature and quality of response, safety, and evolving competitive landscape. If the safety and response data indicate that further evaluation is warranted, up to 18 additional subjects with MF (for a total of up to 30 subjects) will be treated on the same adaptive regimen as was given to the first 12 subjects.
In Part 2 (expansion groups), enrollment of 30 subjects per group offers the opportunity to determine if there is sufficient antitumor activity to warrant further development in the selected tumor types. An ORR of $\geq$ 20% is considered the minimum value of potential interest in each of the selected indications in Part 2. If $\leq$ 2 subjects in a group experience an objective response, the probability is >0.90 that an ORR of $\geq$ 20% will be excluded for that cancer. If 2 subjects in a group experience an objective response, the upper bound of a 1-sided exact binomial 90% CI is 16.8%.

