9 STATISTICAL METHODS OF ANALYSIS

9.1 General Principles

Descriptive statistics will be used to summarize baseline demographic and disease characteristics, study drug administration, efficacy and safety outcomes. Descriptive summaries of discrete data will present the sample size and the incidence as a frequency and as a percentage. Descriptive summaries of continuous data will present

the sample size, group mean, standard deviation (SD), median, and range. Confidence intervals (CIs) may be included as appropriate.

Summary tables will be presented by disease types: CLL/SLL, MCL, WM, FL, GCB DLBCL, MM, non-GCB DLBCL, RICHTER's and Other (include unclassifiable DLBCL, double hit lymphoma, FL with transformation, mediastinal DLBCL, mediastinal gray zone lymphoma, non-hodgkin's lymphoma [NHL], non-mediastinal gray zone lymphoma, red pulp small B-cell lymphoma, triple hit high grade NHL, hodgkin's lymphoma, marginal zone lymphoma), unless otherwise stated.

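### In the pooled Other B-cell malignancy group, the Part 2 statement that a low responder count excludes a 20% ORR holds for the average of the mix, not in general for any single cancer

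*Protocol*

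**What the plan says.** The Statistics part of the protocol synopsis sets one benchmark for Part 2: an ORR of at least "20% is considered the minimum value of potential interest in each of the selected indications in Part 2". It says that "enrollment of 30 subjects per group offers the opportunity to determine if there is sufficient antitumor activity", and that if two or fewer "subjects in a group experience an objective response, the probability is >0.90 that an ORR of" at least 20% "will be excluded for that cancer". As support it adds that, with 2 responders, "the upper bound of a 1-sided exact binomial 90% CI is 16.8"%. Protocol 5.2 and SAP 3.2 repeat the statement for each cohort, but with fewer than two responders as the trigger.

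The synopsis and Protocol 3.0 describe the Part 2 groups as up to 30 subjects per histology. The list of groups nevertheless ends with "Other B-cell malignancy (including but not limited to: Hodgkin's lymphoma, Burkitt lymphoma, marginal zone lymphomas, mediastinal large B-cell lymphoma, and hairy cell leukemia"). The Part 2 cap of 270 equals 9 × 30, which fits non-GCB DLBCL, GCB DLBCL, Richter's syndrome, MCL, FL, WM, CLL/SLL, MM and Other, so Other counts as a single group of 30.

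SAP 9.1 also treats it as one summary category: "Other (include unclassifiable DLBCL, double hit lymphoma, FL with transformation, mediastinal DLBCL, mediastinal gray zone lymphoma", followed by six further entries, 11 in all. SAP 9.6.1.2 plans no response table by histology within Other, and SAP 9.6.2 to 9.6.5 summarise DOR, PFS, time to next treatment and OS by disease group. The documents give no minimum or cap per histology within Other, no separate rule for it and no caveat on the single-cancer wording.

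**The concern.** The exact binomial bound concerns the response rate of the subjects who were counted. In a group made up of one histology, that is the rate for a cancer. In Other, it is the average rate over whatever mix was enrolled. The plan nonetheless draws the conclusion at the level of a single cancer in every group.

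What is at stake is interpretation at reporting. The stated purpose of the 30-subject groups is to judge whether activity justifies further development in the selected tumour types. A low pooled count in Other could be read as ruling out a 20% ORR in Hodgkin's lymphoma or marginal zone lymphoma, say, on the strength of a handful of such subjects. With no table by histology planned, the report would give the reader no summary against which to check that reading.

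**Working it through.** **Inputs.** Benchmark 20%, group size 30, trigger ≤2 responders, one-sided exact 90% bound of 16.8% at 2/30, and the stated probability above 0.90 (all from the synopsis). Alternative trigger <2 (Protocol 5.2, SAP 3.2). Contents of Other: five named diseases, open-ended (synopsis), or 11 listed entities (SAP 9.1). The number of subjects per histology is not given, so every split below is an assumption.

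**Step 1: reproduce the plan's figure.** The one-sided 90% Clopper-Pearson upper bound for x responders in n subjects is the 0.90 quantile of Beta(x+1, n−x).
- x=2, n=30: 16.8%, as stated.
- P(X≤2 | n=30, p=0.20) = 0.044, so the confidence of exclusion is 1 − 0.044 = 0.956, above 0.90.
- x=3, n=30: 20.9%, so 2 is the largest count that excludes 20%.

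The plan's figure is right for a group with one response rate.

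**Step 2: what the pooled bound means in a mixed group.** Keep the mean rate at 20%, let the members differ, and compute P(X≤2) from sums of independent binomials:

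| Mix of 30 (mean 20%) | P(≤2) |
|---|---|
| 30 at 20% | 0.044 |
| 15 at 30%, 15 at 10% | 0.039 |
| 10 at 40%, 20 at 10% | 0.035 |
| 12 at 50%, 18 at 0% | 0.019 |

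Heterogeneity lowers the probability, so the exclusion stays valid for the average rate of the mix.

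**Step 3: what it means for one histology.** Let a histology with a true ORR of 20% supply m of the 30, and let the other 30 − m respond at rate q. The total is Bin(m, 0.20) + Bin(30−m, q). The probability that the count meets the rule is:

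| m | q | P(≤2), synopsis | P(<2), Protocol 5.2 and SAP 3.2 |
|---|---|---|---|
| 3 | 0% | 0.992 | 0.896 |
| 6 | 0% | 0.901 | 0.655 |
| 10 | 0% | 0.678 | 0.376 |
| 3 | 5% | 0.692 | 0.406 |
| 6 | 5% | 0.563 | 0.288 |
| 10 | 5% | 0.405 | 0.175 |

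If the statement held for that cancer, each entry would be at most 0.10. The lowest is 0.175.

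**Step 4: how many subjects one histology needs.** One-sided 90% upper bounds:
- 0/10: 20.6%; 0/11: 18.9%.
- 1/18: 19.9%.
- 2/25: 19.9%.

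The smallest numbers that exclude 20% are therefore 11, 18 and 25 subjects with 0, 1 and 2 responders. An even split over the five named diseases gives 30/5 = 6 each, and 0/6 leaves a bound of 31.9%. An even split over the 11 SAP entries gives 30/11 ≈ 2.7 each; 0/3 leaves 53.6% and 0/2 leaves 68.4%.

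**Step 5: an illustration.** Two responders among 4 subjects of one histology and none among the other 26 make 2/30, which meets the synopsis version. The exact two-sided 90% interval for 2/4 is 9.8% to 90.2%. The <2 version would not be met here.

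**The case against.** Four objections carry weight.

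- *The bound is valid for what it measures.* Step 2 confirms this for the average rate. The mixes in Step 3 have true average rates of only 2% to 10%, so a low pooled count there is correct for the group. This stands. The fault is confined to carrying the group result over to a single cancer.
- *The absolute reading fails.* A reader might infer that the rule can exclude 20% for no individual cancer in Other, or that the pooled count carries no information about its members. Neither follows. A histology with 0/11, 1/18 or 2/25 is excluded, and a total of at most 2 caps every member at 2 responders. The 11 SAP entries are also not 11 clearly separate cancers: one is NHL in general, and several are closely related. No passage supports an even split.
- *Nothing is decided at this count.* A reader might infer a formal stop or go rule for Part 2. There is none. Unlike Part 3, where fewer than 2 responders among the first 12 means no expansion, Part 2 attaches no action to a count. SAP 5 states that no formal hypothesis is tested, and SAP 7 that no formal interim analysis was planned. Nor does the rule award activity to anyone, since it only excludes.
- *Enrolment is over and safety is primary.* Protocol 5.1 reports closure in May 2017 with 161 evaluable subjects and allows analyses by cancer type as appropriate. No design change can follow. That general permission is not a planned table, however, and SAP 9.1 specifies Other as one category.

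What remains is a claim about interpretation that the plan makes and that does not hold in general for this group.

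**Conclusion.** The point holds in a limited form. For Other B-cell malignancy, the statement supports excluding 20% for the average of the enrolled mix. It supports the same for one histology only if that histology is large enough (at least 11 subjects with no responders, 18 with one, 25 with two). Otherwise the stated confidence does not apply. A histology with a true 20% ORR supplying 3 to 10 of 30 would be declared excluded with probability 0.41 to 0.99 under ≤2, or 0.18 to 0.90 under <2, rather than at most 0.10.

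These ranges rest on an assumed mix, response rates of 0% to 5% in the other histologies, independent responses and a full group of 30. The documents give neither the mix nor the final size of Other. The difference between ≤2 in the synopsis and <2 in Protocol 5.2 and SAP 3.2 is a separate inconsistency, and the conclusion is the same under either. The consequence is limited to how activity in individual tumour types is reported. The primary safety analysis and the single-histology groups are unaffected by this point.

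**What to change.** 1. In the synopsis, Protocol 5.2 and SAP 3.2, limit the single-cancer exclusion statement and the 16.8% bound to the single-histology groups. State that for Other the bound describes only the mixed group.
2. In SAP 9.6.1.2, add responders n/N with an exact CI for each histology within Other, using the list in SAP 9.1.
3. Label pooled ORR, DOR, PFS and OS for Other as descriptive of a mixed group.

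The cost is wording in three places, labels on the pooled outputs and one extra table. It uses data already collected. The downside is small: the intervals by histology will be wide, and Other will carry no single-cancer exclusion statement.

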#### 1.0 BACKGROUND INFORMATION

#### 1.1 A CASE FOR COMBINATION BTK AND CHECKPOINT BLOCKADE FOR TREATMENT OF HEMATOLOGIC MALIGNANCIES

Through decades of clinical experience, the use of multidrug regimens has been shown to produce higher CR rates and more durable responses, resulting in improved survival in most oncology indications. However, these benefits are often outweighed with the increased toxicity associated with multidrug regimens. This high risk-benefit ratio limits the use of many effective multidrug regimens in elderly patients or patients with comorbid conditions.

The advent of highly selective, targeted agents such as BTK inhibitors has changed the risk-benefit paradigm traditionally associated with cytotoxic chemotherapy regimens. For example, ibrutinib, a first-generation oral, small-molecule BTK inhibitor, has been approved for the treatment for CLL and MCL (IMBRUVICA Package Insert). In addition, ibrutinib has shown clinical efficacy in other NHL histologies, including FL (Advani 2013), DLBCL (De Vos 2013), and in WM (Treon 2013). Preliminary data suggests that patients with MM with high BTK activity, as evidenced by phosphorylated BTK, may be particularly responsive to BTK inhibitor therapy (Liu 2014). In nonclinical studies, BTK inhibition significantly reduced MM cell growth and tumor-induced osteolysis in a murine model (Tai 2012). Despite these significant advances, the investigation of additional treatment regimens is essential to improve outcomes in hematologic malignances. A low proportion of patients achieve CR when treated with single-agent BTK inhibitors compared with conventional chemotherapy or chemoimmunotherapy regimens. Moreover, the median duration of response can be brief (<12 months) in aggressive histologies.

Chemical optimization, pharmacologic characterization, and toxicologic evaluation have led to identification of acalabrutinib, an orally administered, new chemical entity that covalently inhibits BTK and shows encouraging activity and acceptable safety in nonclinical studies. Within the class of BTK inhibitors, acalabrutinib is a more selective inhibitor of BTK than ibrutinib. Key nonclinical differentiators of acalabrutinib versus ibrutinib are:

 Acalabrutinib has been evaluated against ibrutinib in epidermal growth factor receptor (EGFR) expressing cell lines. Ibrutinib is a potent covalent inhibitor of EGFR (EC50=5.3 nM). Acalabrutinib did not inhibit EGFR, even at the highest concentration tested (10 µM).

- Acalabrutinib and ibrutinib have been evaluated in natural killer (NK) cell functional assays. While ibrutinib inhibits NK cell functions including antibody-dependent cellular cytotoxicity (ADCC), lytic granule release and cytokine production (Kohrt 2014), the in vitro functional activity of acalabrutinib-treated NK cells was preserved.
- Acalabrutinib has been evaluated against ibrutinib in an in vivo thrombus formation model. Platelets from CLL patients treated with acalabrutinib had similar thrombus formation dynamics as platelets from healthy volunteers, while platelets from ibrutinib-treated CLL patients had impaired thrombus formation.

[figure not shown]
The nonclinical and toxicology results of acalabrutinib suggest it may have an improved therapeutic window relative to ibrutinib; it may be more readily combined with other agents for the treatment of cancer including monoclonal antibodies that activate effector cells.

Improved understanding of the molecular mechanisms governing the host response to tumors has led to the identification of checkpoint signaling pathways involved in limiting the anticancer immune response (Topalian 2011). A critical checkpoint pathway responsible for mediating tumor-induced immune suppression is the PD-1 pathway

(McDermott and Atkins 2013). This proof-of-concept study will assess the clinical potential of combined BTK inhibition and checkpoint blockade by evaluating the safety, PD, and efficacy of acalabrutinib and pembrolizumab in hematologic malignancies.

To determine whether there is potential synergy between BTK inhibition and PD-1 blockade, Acerta conducted a nonclinical study of acalabrutinib in combination with an anti–PD-L1 antibody in an orthotopic colon cancer murine model. Mice were inoculated with syngeneic CT26 colorectal cancer cells on Day 0; anti–PD-L1 (150 µg on Days 6, 9, 12, 15) and acalabrutinib (15 mg/kg BID) treatment was initiated on Day 6, when the tumor was well established. Treatment of mice with ACP-196 alone did not substantially diminish tumor growth. In comparison, there was a significant reduction in tumor volume in mice treated with the PD-L1 antibody (mean + SD of 621 +349 mm^3) or the combination of ACP-196 + PD-L1 antibody (mean + SD of 491 +489 mm^3) compared to tumor sizes in the untreated group (mean + SD of 2667 +1222 mm^3, p<0.0001) or ACP-196 only group (mean + SD of 2449 +1149 mm^3, p=0.0004) (see Figure 1). On Day 14, the average tumor growth was not significantly different between mice treated with the PD-L1 antibody or the combination of ACP-196 + PD-L1 antibody (see Figure 1). Interestingly, in the combination group, 5 of 10 tumors appeared to be smaller than any of those in the PD-L1 antibody-treated group (see Figure 1). Additionally, there were 2 complete regressions (CRs) in the combination-treated group but not in the PD-L1 antibody group (see Figure 1).

#### Figure 1 Acalabrutinib Enhances the Antitumor Effects of α-PD-L1 in the Orthotopic CT26 Colon Cancer Model

ACP-196=acalabrutinib; CR=complete regression; PD-L1=programmed death ligand-1. Effects of ACP-196 or anti-PD-L1 antibody alone or in combination were evaluated in the CT26 colorectal tumor model in Balb/c mice. A) Treatment effects on tumor growth, and B) Treatment effects on Day 14. Data were available from 9 mice in the ACP-196 group and10 mice in the other groups on Day 14. Data analyzed by one-way analysis of variance (ANOVA) with Sidak's multiple comparison test (\*\*\*p=0.0002 to ACP-196, \*\*\*\*p<0.0001 to Untreated).

Summaries of other nonclinical and clinical studies for acalabrutinib are provided below. For more detailed information refer to the acalabrutinib Investigator Brochure (IB). For detailed information on pembrolizumab refer to the pembrolizumab (MK-3475) IB.

# 1.2 ACALABRUTINIB

Acalabrutinib is an imidazopyrazine analogue with a molecular weight of 465.5 g/mol. The compound has 1 stereogenic center and acalabrutinib is the S-enantiomer. Acalabrutinib is orally administered and is suitable for formulating in capsules. For clinical testing, acalabrutinib has been manufactured and formulated according to current Good Manufacturing Practices (cGMP).

Acalabrutinib (CALQUENCE®) is an investigational product. CALQUENCE® has been approved in the United States and other markets for the treatment of adult patients with mantle cell lymphoma (MCL) who have received at least one prior therapy, chronic lymphocytic leukemia (CLL), and small lymphocytic lymphoma (SLL).

## 1.2.1 Mechanism of Action

Acalabrutinib is a highly selective, potent, covalent inhibitor of BTK. In kinase activity assays and wide kinome screens, acalabrutinib was more selective than ibrutinib (Covey 2015). For additional details, refer to the acalabrutinib IB.

## 1.2.2 Spontaneous Canine B-cell Lymphoma

[figure not shown]
Spontaneous canine B-cell lymphoma shares many characteristics with human NHL, including diagnostic classifications and response to BTK inhibition (Honigberg 2010). The life expectancy in untreated animals with aggressive disease is ~6 weeks, thus enabling rapid assessment of drug efficacy (Vail 2004). Acalabrutinib was evaluated in a dose-escalation study in canine spontaneous B-cell lymphoma (Harrington 2016). Twenty dogs were enrolled in the clinical trial and treated with acalabrutinib at dosages of 2.5 to 20 mg/kg every 12 or 24 hours. Acalabrutinib was generally well tolerated, with AEs consisting primarily of Grade 1 or 2 anorexia, weight loss, vomiting, diarrhea, and lethargy. Per Veterinary Cooperative Oncology Group criteria for assessment of response in peripheral nodal lymphoma (Vail 2010), the ORR was 25% (5/20) with a median progression-free survival of 22.5 days. Clinical benefit was observed in 30% (6/20) of dogs. These findings suggest that acalabrutinib is safe and exhibits activity in canine B-cell lymphoma patients and support the use of canine lymphoma as a relevant model for human NHL. These findings are similar to the clinical responses observed with ibrutinib in dogs with spontaneous B-cell lymphoma (Honigberg 2010).

### 1.2.3 Acalabrutinib and Antibody-dependent Cell-mediated Cytotoxicity

As acalabrutinib is not an inhibitor of interleukin-2-inducible kinase (ITK), it is expected to have less activity against non-malignant cells that require ITK for development and functional activation, such as T and NK cells. ITK kinase is required for FcR-stimulated NK cell functions including calcium mobilization, lytic granule release (Khurana 2007), and overall ADCC. Anti-CD20 antibodies are standard of care drugs, often as part of combination regimens, for the treatment of CD20+ B-cell malignancies; obinutuzumab has

been specifically designed to increase Fc interactions and promote ADCC and phagocytosis of malignant CD20+ cells. Ibrutinib has been evaluated for effects on NK activity, including ADCC, using in vitro assays of cytokine release, lytic granule release, and cellular cytotoxicity (Kohrt 2014). In contrast to more specific BTK inhibitors, ibrutinib inhibited all these NK cell functions, and impaired NK activity against rituximab-coated autologous CLL cells and in mouse tumor models requiring Fc-mediated effector functions (Kohrt 2014). Acalabrutinib was tested in ADCC and natural cytotoxicity assays, using cells from healthy donors. In these in vitro tests, NK cell function was preserved with acalabrutinib treatment, whereas ibrutinib inhibited functional activity, including natural cytotoxicity against K562 cells.

#### Figure 2 NK Cell Natural Cytotoxicity

[figure not shown]

Peripheral blood mononuclear cells were cultured with Cr labelled K562 targets at an effector-to-target (E:T) ratio of 100:1 for 4 hours. Cytotoxicity was evaluated by scintillation counting of supernatants. Treatment, dose, and interaction effect were significant in 2-way analysis of variance (ANOVA) (n=5 healthy donors; ibrutinib versus acalabrutinib p<0.0001; all ibrutinib doses p<0.0001 compared with control; p=0.0117 for control versus acalabrutinib 1  $\mu$ M, other acalabrutinib doses not statistically different from control condition).

